9.0 PATIENT EVALUATION (See Appendix AA)

9.1 Pre-Treatment Evaluation

All pretreatment studies should be obtained within 14 days of entry into the trial, unless otherwise stated.

- 9.1.1 A complete history and physical, documentation of all measurable disease, concomitant medications and performance status.
- 9.1.2 CBC, platelet count, differential (differential can be omitted if WBC is $\leq 0.5 \times 10^9/L$).
- 9.1.3 Creatinine, total bilirubin, ALT, potassium, magnesium, calcium, sodium, chloride, CO₂, uric acid, phosphorus, and BUN.
- 9.1.4 Pregnancy test (urine or plasma) in females of childbearing potential, should be performed 48 hours before initiation of study.
- 9.1.5 Bone marrow aspirate during the last 21 days preceding study initiation. Cytogenetics will be obtained prior to therapy (results from prior analysis can be used for this purpose).
- 9.1.6 Evaluation of FLT3 if not done within 90 days, provided there has been no intervening therapy other than hydroxyurea or isolated single-agent doses of cytarabine.
- 9.1.7 EKG and ECHO and/or MUGA will be performed before initiating study treatment if not done within 28 days.
- 9.1.8 Pretreatment optional correlative studies (see Section 8.0)

9.2 Evaluation During Treatment

- 9.2.1 Physical exam at the start of each cycle (± 5 days) for the first 2 cycles, then every 2-3 cycles and documentation of all concomitant medications.
 - 9.2.1.1 Patients will keep a diary for drug administration of self-administered drugs (cytarabine and AC220)
- 9.2.2 CBC, platelet count, differential once weekly for the first 3 cycles, then every 2-4 weeks (all ± 2 days) (differential can be omitted if WBC is $\leq 0.5 \times 10^9/L$)
- 9.2.3 Creatinine, total bilirubin, ALT, K, Mg, Ca, sodium, chloride, and CO₂ on day 5 prior to start of AC220, then weekly for the first 3 cycles, then every 2-4 weeks (all ± 2 days) .
- 9.2.4 Bone marrow aspiration on day 28 (± 7 days) of cycle 1, then every 1-3

cycles.

9.2.5 EKG will be performed on day 1, day 5, day 8, and day 12 of the first cycle (all ± 2 days) Day 1 and day 8 ECG are collected pre-dose; day 5 are collected pre-dose and 4 hrs (± 2 hrs) post-dose; day 12 are collected 4 hrs (± 2 hrs) post-dose. Then ECG to be done on day 1 of each cycle for cycles 2 and 3 before initiation of quizartinib and 4 hr (± 2 hrs) post dose, then pre-dose every 2-3 cycles. EKG may be omitted if patient has not received study drug (AC220) in the 48 hrs preceding the time when EKG is done. EKG for the first 3 cycles will be done in triplicate. Day 5 pre AC-220 will be used as baseline.

9.2.5.1 On patients in whom quizartinib is escalated to 90 mg daily as described in section 6.5.5 or who start therapy with a drug that may prolong QT/QTc or that is a strong CYP3A4 inhibitor or inducer, an EKG will be required 24 hrs (± 6 hrs), 7 days (± 2 days) and 14 days (± 2 days) after the dose increase or after the start of such drug.

9.2.5.2 Patients who had their dose reduced because of QTc prolongation and have their dose re-escalated as described in section 6.3 will have an EKG repeated 24 hrs (± 6 hrs) and 7 days (± 2 days) after re-escalation.

9.2.5.3 The QTc interval will be calculated by Fridericia's correction factor (QTcF). The 12-lead EKG evaluation will consist of 3 separate EKGs obtained at least 5 minutes apart.

9.2.6 Correlative studies on days 1, 8 and 15 of each cycle up to the first 4 cycles (all ± 2 days). (Optional – See Section 8.0).

9.2.7 For patients that remain on study with no significant toxicity for more than 6 months, subsequent evaluations during study may be modified after discussion with the principal investigator. These include a decrease in frequency of standard laboratory tests to once every cycle, bone marrow aspirations to every 6-12 months (or as clinically indicated).

Outside Physician Participation During Treatment

1. MDACC Physician communication with the outside physician is required prior to the patient returning to the local physician.
*This will be documented in the patient record
2. A letter to the local physician outlining the patient's participation in a clinical trial will request local physician agreement to supervise the patient's care (Appendix E)

3. Protocol required evaluations outside MDACC will be documented by telephone, fax or e-mail. Fax and/or e-mail will be dated and signed by the MDACC physician, indicating that they have reviewed it.
4. Changes in drug dose and/or schedule must be discussed with and approved by the MDACC physician investigator, or their representative prior to initiation, and will be documented in the patient record.
5. A copy of the informed consent, protocol abstract, treatment schema and evaluation during treatment will be provided to the local physician.
6. Documentation to be provided by the local physician will include drug administration records, progress notes, reports of protocol required laboratory and diagnostic studies and documentation of any hospitalizations.
7. The home physician will be requested to report to the MDACC physician investigator all life threatening events within 24 hours of documented occurrence.
8. Patients will return to MDACC approximately every month.

10.0 CRITERIA FOR RESPONSE

Criteria for response will be as per the international working group for MDS and AML.

10.1 Response Criteria for MDS

Response criteria will be according to the International Working Group (Blood 2006; 108: 419-425). Responders are patients who obtain a CR, CRi, or PR, with or without cytogenetic response, hematologic improvements, and morphologic leukemia-free state. Briefly, criteria are as follows:

10.1.1 *Morphologic Complete Response (CR)*

- ◆ **Peripheral blood counts:**
No circulating blasts
Neutrophil count $\geq 1.0 \times 10^9/L$
Platelet count $\geq 100 \times 10^9/L$
- ◆ **Bone marrow aspirate and biopsy:**
 $\leq 5\%$ blasts
No extramedullary leukemia

10.1.2 **Partial Response (PR)**

- ◆ All CR criteria if abnormal before treatment except:
- ◆ $\geq 50\%$ reduction in bone marrow blast but still $>5\%$

10.1.3 **Marrow CR**

- ◆ Bone marrow: $\leq 5\%$ myeloblasts and decrease by $\geq 50\%$ over pretreatment

- ◆ Peripheral blood: if HI responses, they will be noted in addition to marrow CR

10.1.4 Hematologic Improvement (HI): Hematologic response must be described by the number of positively affected cell lines.

- ◆ **Erythroid response (E)** (pretreatment Hgb <11 g/dL)
Hgb increase by ≥ 1.5 g/dL
- ◆ **Platelet response (P)** (pretreatment platelets <100 $\times 10^9/L$)
Absolute increase of $\geq 30 \times 10^9/L$ for patients starting with $> 20 \times 10^9/L$ platelets
Increase from $< 20 \times 10^9/L$ to $> 20 \times 10^9/L$ and by at least 100%
- ◆ **Neutrophil response (N)** (pretreatment ANC <1.0 $\times 10^9/L$)
At least 100% increase and an absolute increase $> 0.5 \times 10^9/L$

10.2 Response Criteria for AML

Response criteria will be modified from the International Working Group for AML (JCO 2003; 21: 4642-9). Responders are patients who obtain a CR, CRi, or PR, with or without cytogenetic response, hematologic improvements, and morphologic leukemia-free state. Briefly, criteria are as follows:

10.2.1 Complete remission (CR):

- ◆ **Peripheral blood counts:**
No circulating blasts
Neutrophil count $\geq 1.0 \times 10^9/L$
Platelet count $\geq 100 \times 10^9/L$
- ◆ **Bone marrow aspirate and biopsy:**
 $\leq 5\%$ blasts
No Auer rods
No extramedullary leukemia

10.2.2 Complete remission with incomplete blood count recovery (CRi):

- ◆ **Peripheral blood counts:**
No circulating blasts
Neutrophil count $< 1.0 \times 10^9/L$, and/or
Platelet count $< 100 \times 10^9/L$
- ◆ **Bone marrow aspirate and biopsy:**
 $\leq 5\%$ blasts

No Auer rods
No extramedullary leukemia

10.2.3 Partial remission:

- ◆ All CR criteria if abnormal before treatment except:
- ◆ $\geq 50\%$ reduction in bone marrow blast but still $> 5\%$

10.2.4 Morphologic leukemia-free state:

- ◆ Bone marrow: $\leq 5\%$ myeloblasts

10.2.5 Hematologic Improvement (HI): Hematologic response must be described by the number of positively affected cell lines.

- ◆ **Erythroid response (E)** (pretreatment Hgb < 11 g/dL)
Hgb increase by ≥ 1.5 g/dL
- ◆ **Platelet response (P)** (pretreatment platelets $< 100 \times 10^9/L$)
Absolute increase of $\geq 30 \times 10^9/L$ for patients starting with $> 20 \times 10^9/L$ platelets
Increase from $< 20 \times 10^9/L$ to $> 20 \times 10^9/L$ and by at least 100%
- ◆ **Neutrophil response (N)** (pretreatment ANC $< 1.0 \times 10^9/L$)
At least 100% increase and an absolute increase $> 0.5 \times 10^9/L$
- ◆ **Blast response (BI)** a $\geq 50\%$ reduction in blast percentage in bone marrow and/or $\geq 50\%$ reduction in peripheral blood total blast count.

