4.1.4 For Phase I and II

4.1.4.1 ECOG Performance Status ≤ 2

4.1.4.2 Adequate liver (bilirubin $\leq 2x$ ULN, ALT $\leq 2.5x$ ULN) and renal (creatinine $\leq 2x$ ULN) function. For patients with suspected liver infiltration from leukemia, ALT should be $\leq 5x$ ULN.

4.1.4.3 Serum potassium, magnesium, and calcium (normalized for albumin) levels should be at least within institutional normal limits.

4.1.4.4 Patients must provide written informed consent.

4.1.4.5 Patients must have been off chemotherapy for 2 weeks prior to entering this study, unless there is evidence of rapidly progressive disease, and must have recovered from the toxic effects of that therapy to at least grade 1. Use of hydroxyurea for patients with rapidly proliferative disease is allowed before the start of study therapy and for the first four weeks on therapy. The additional days of Hydrea after 28 is permitted as clinically indicated, on case by case basis and after discussion with the PI. Other agents given transiently with the intention to control rapid proliferation such as 1-2 doses of single agent ara-C or few doses of sorafenib are also allowed.

4.1.4.6 Women of childbearing potential must practice contraception. Women considered not of childbearing potential include any of the following: no menses for at least 2 years or menses within 2 years but amenorrheic for at least 2 months and luteinizing hormone (LH) and follicular stimulating hormone (FSH) values within normal range (according to definition of postmenopausal for laboratory used) or bilateral oophorectomy or radiation castration and amenorrheic for at least 3 months. Females of childbearing potential should practice effective methods of contraception. Effective methods of contraception include barrier methods (e.g., condoms, diaphragm), spermicidal jelly or foam, oral, depo provera, or injectable contraceptives, intrauterine devices, tubal ligation, and abstinence. Male patients with female partners who are of childbearing potential should also practice contraception.

4.1.5 Negative urine or serum pregnancy test.

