5.4 Concomitant Medications

5.4.1 The use of any concomitant medication/therapies deemed necessary for patient supportive care and safety are permitted. Other anticancer agents including systemic chemotherapy, radiation therapy, or biologic response modifiers are not permitted during the study. No other investigational drug is allowed during the study. Patients must be off growth factors for five days in order to declare a neutrophil response. Antiemetics may be used for the prevention or treatment of nausea and vomiting.

5.4.2 The administration of drugs known to prolong QTc interval or strong CYP3A4 inhibitors should be administered with caution. Any drug known to inhibit or induce CYP3A4 will likely interact with quizartinib.

The list of drugs that can be associated with Torsades de Pointes or prolonged QT interval can be found online at:

<http://www.azcert.org/medical-pros/drug-lists/bycategory.cfm>.

The list of drugs that interact with CYP3A4 can be found online at:

<http://medicine.iupui.edu/clinpharm/DDIs/ClinicalTable.aspx>

5.4.3 Administration of other antineoplastic agents is prohibited for patients while on this study with the following exceptions: 1) Hydroxyurea may be

used for the first 28 days of therapy. The additional days of Hydrea after 28 days is permitted as clinically indicated, on case by case basis and after discussion with the PI . 2) Administration of intrathecal chemotherapy is allowed when clinically indicated.

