12.3 Phase II

A: Cohort 2A – FLT3-ITD

The primary endpoint of the phase II portion of the study is overall response (CR+Cri+PR+HI) (first 2 treatment courses). It would be encouraging if the overall response rate reaches 50%.

Treatment with AC220 + low-dose cytarabine (Cohort 2A-FLT3-ITD)

Patients enrolled in the treatment of AC220 + low-dose cytarabine could be newly diagnosed or previously treated. A total of 26 patients (including 6 patients treated at MTD in Phase I) will be treated with this treatment combination. The toxicity and efficacy (CR+Cri+PR+HI) will be monitored during the study, and all the data will be used to update the prior distributions for toxicity and efficacy parameters. The study will be stopped for toxicity and futility based on the following stopping rules. If the trial for this treatment continues until 26 patients are evaluated, and assuming the overall response rate is 50%, then the 95% credible interval for overall response rate would be (0.32, 0.68).

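### Section 12.3 counts hematologic improvement alone as a primary response although section 10 reads otherwise, and the written HI rules do not exclude effects of hydroxyurea or transfusion

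*Combined protocol and SAP*

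**What the plan says.** - Section 12.3, under Cohort 2A: "The primary endpoint of the phase II portion of the study is overall response (CR+Cri+PR+HI) (first 2 treatment courses"). The futility rules in that section run on this response count.
- Sections 10.1 and 10.2 each open by describing responders as patients who reach CR, CRi or PR. HI appears there only among features that may or may not be present as well.
- Section 10.2.5 (AML) lists four HI components. The blast component is met by a fall of at least 50% in marrow blast percentage, or by a "reduction in peripheral blood total blast count" of the same size, either being enough. The erythroid component is "Hgb increase by" at least 1.5 g/dL from a baseline below 11. The platelet component is a rise of at least 30 x 10^9/L "for patients starting with" more than 20 x 10^9/L, or a doubling from below 20 to above 20. The neutrophil component is a doubling with an absolute rise above 0.5 x 10^9/L.
- Section 10.1.4 (MDS) repeats the erythroid, platelet and neutrophil components and has no blast component.
- Section 10.2 on its source: "Response criteria will be modified from the International Working Group for AML". Both sets of criteria are given in brief.
- Section 4.1.4.5: "Use of hydroxyurea for patients with rapidly proliferative disease is allowed before the start of study therapy and for the first four weeks on therapy". Section 5.4.3: "The additional days of Hydrea after 28 days is permitted as clinically indicated", case by case after discussion with the PI.
- Section 5.4.1 allows any supportive therapy judged necessary. It also contains the only washout tied to response: "Patients must be off growth factors for five days in order to declare a neutrophil response".

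**The concern.** Two things are unsettled in the primary endpoint.

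First, the documents do not agree on whether HI alone makes a patient a responder. Section 12.3 says it does; the opening of section 10 reads as if it does not.

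Second, if HI does count, the written rules do not separate an effect of the combination from an effect of permitted co-treatment. Hydroxyurea is given to control proliferation, so it acts on the peripheral blast count, and a transfusion raises the hemoglobin or platelet count being scored. Both can fall inside the two-course window. The plan guards against this kind of confounding for neutrophils only.

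The response rate is judged against 50% in Cohort 2A, and no reference rate on the same composite is given. It also drives the futility rule. Responses that do not reflect the combination would raise the estimate and make a group with too little activity less likely to stop.

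**Working it through.** **1. Where a condition could have been written.** Sections 10.1.4, 10.2.5, 12.3 and 12.4 and Appendix AA contain no minimum duration, repeat assessment, transfusion-free interval or hydroxyurea-free interval for HI. Section 5.4.1 adds five days off growth factors, for the neutrophil component only.

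| HI component | AML (10.2.5) | MDS (10.1.4) | Permitted co-treatment acting on it | Washout written |
|---|---|---|---|---|
| Peripheral blasts | yes | not listed | hydroxyurea | none |
| Hemoglobin | yes | yes | red-cell transfusion | none |
| Platelets | yes | yes | platelet transfusion | none |
| Neutrophils | yes | yes | growth factors | 5 days |

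**2. Timing.** The window is two courses of 28 days. Hydroxyurea is allowed for the first 28 days, which is all of course 1, and may extend into course 2 case by case.

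**3. Reproducing the plan's figures (Cohort 2A, azacitidine).** With a beta(1,1) prior and r responses in n patients, the posterior is beta(1+r, 1+n−r). The rule stops if Pr(P_E < 0.5 | data) > 0.98. At 3/15 the posterior is beta(4, 13) and the probability is 0.989, so the rule stops. At 4/15 it is beta(5, 12) and 0.962, so it continues. All the printed futility boundaries (3/15, 5/20, 7/25, 9/30, 11/35, 13/40, 15/45) and toxicity boundaries (8/15 to 18/45) reproduce this way.

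An exact binomial recursion over the seven looks, with response and toxicity independent, gives early stopping at toxicity 0.1 of 0.993, 0.584 and 0.055 for response rates 0.2, 0.35 and 0.5. Average sizes are 18.6, 35.8 and 48.6. These match the section 12.3 table for this design. The arithmetic is sound; the question is what is counted.

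**4. Illustration.** Let q be the response rate without artefact and m the share of the remaining patients scored as HI only because of hydroxyurea or transfusion. The observed rate is q + (1−q)m. Neither q nor m is in the documents. Assume q = 0.40 and add 5, 10 or 15 points, so m = 0.05/0.60 = 8.3%, 0.10/0.60 = 16.7% or 0.15/0.60 = 25%. The same boundaries at toxicity 0.1 give:

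| Artefact (points) | Observed rate | Probability of early stopping |
|---|---|---|
| 0 | 0.40 | 0.336 |
| 5 | 0.45 | 0.153 |
| 10 | 0.50 | 0.055 |
| 15 | 0.55 | 0.016 |

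For the 26-patient cytarabine group, the plan's own operating-characteristics table shows the same step: stopping is 0.175 at a rate of 0.4 and 0.038 at 0.5, with toxicity 0.1.

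**The case against.** **The cited criteria may supply the missing conditions.** Section 10 says responses follow the international working group, and both lists are given in brief. The erythroid, platelet and neutrophil rules are the same in the AML and MDS lists, and the MDS list is said to follow its source. A reader might infer from the word modified in section 10.2 that safeguards were deliberately dropped for AML. The documents do not support that: they do not say which items were modified, and the sources are not reproduced. What can be said is that no condition is written here, so the endpoint cannot be scored from the protocol alone.

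**HI may not count alone.** This is a fair reading of the responder sentence in section 10. It does not remove the point, because section 12.3 states the composite explicitly and the stopping rules depend on it. A reader should not take either version as settled.

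**The effect may be small.** Hydroxyurea is for rapidly proliferative disease and needs PI discussion beyond day 28. Given before study start, it could also lower the baseline blast count and make a further 50% fall harder to reach. This stands as a limit on size. Direction is unaffected: counting HI without these conditions can add responders and cannot remove any.

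**Cohort 2B.** A reader might infer that the comparison of 45% with 30% is affected in the same way. Section 12.3 spells out the composite under Cohort 2A and does not define response for Cohort 2B, nor say whether the 30% counted HI. Its use there is an inference from the phrase about the phase II portion of the study.

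**Conclusion.** The concern holds in this form. Sections 10 and 12.3 must be reconciled on whether HI alone is a response. If it is, the written HI rules allow a peripheral blast fall on hydroxyurea, or a count rise after transfusion, to score as a primary response. The blast gap is specific to AML; the transfusion and confirmation gap applies to AML and MDS alike.

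The documents support the direction: a response rate that can be too high and a futility rule that can be too lenient. They give no HI-only rate, so the fall in early stopping from 0.34 to 0.055 (0.15 to 0.016 for 5 to 15 points) is illustrative. It rests on an assumed true rate of 40%, the assumed artefact share, toxicity 0.1, and independence of response and toxicity. It is not an estimate of bias in this trial. The change should be made, because the endpoint is open to two readings and the looser one feeds the stopping rules.

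**What to change.** 1. Reconcile the responder sentences in sections 10.1 and 10.2 with section 12.3, and state the response definition for Cohort 2B.
2. In both 10.1.4 and 10.2.5, do not count a hemoglobin or platelet rise attributable to transfusion. In 10.2.5, do not count a peripheral blast fall while the patient is on hydroxyurea. This changes scoring only, not treatment.
3. Have the sponsor state the interval and confirmation for each component. The five-day growth-factor interval should not simply be carried over: the documents give no reason that it suits red-cell transfusion. Marrow blasts should be confirmed on the scheduled marrow (section 9.2.4), not a blood count. For peripheral blasts, note that the differential may be omitted when WBC is at or below 0.5 x 10^9/L (section 9.2.2).
4. Report CR+CRi+PR without HI beside the primary result and at each futility look.

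Cost: a somewhat lower response rate, wording in sections 10 and 12.3, and some data work. Blood counts are scheduled weekly for the first three cycles, but transfusions are not a listed assessment, concomitant medications are scheduled at cycle starts, and section 11.4 keeps abnormal hematologic values off the case report form. Transfusion dates and serial counts may therefore have to come from source records. Item 4 needs no new data beyond the response category.

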11.0 ADVERSE EVENT REPORTING

11.1 Adverse event is any untoward medical occurrence that may present during treatment with a pharmaceutical product but which does not necessarily have a causal relationship with this treatment. Adverse drug reaction is a response to a drug which is noxious and unintended and which occurs at doses normally used in man for prophylaxis, diagnosis, or therapy of disease or for the modification of physiologic function.

Assessing causal connections between agents and disease is fundamental to the understanding of adverse drug reactions. In general, a drug may be considered a contributory cause of an adverse event if, had the drug not been administered, 1) the event would not have happened at all, 2) the event would have occurred later than it actually did, or 3) the event would have been less severe.

The Investigator or physician designee is responsible for verifying and providing source documentation for all adverse events and assigning the attribution for each event for all subjects enrolled on the trial.

- 11.2 PDMS/CORe will be used as the electronic case report form for this protocol. Adverse events will be documented in the medical record and entered into PDMS/CORe.
- 11.3 Adverse Events (AEs) will be evaluated according to the latest CTC version and documented in medical record. All suspected adverse drug reactions (SADR) will be recorded in the Case Report Form (CRF). Expected events during leukemia therapy are:

